## **III. Subject Selection:**

This study is a randomized, double-blind, placebo-control trial. The trial will enroll 74 adult subjects with treatment-refractory major depressive disorder, 37 per group. Assuming a non-completion rate of approximately 20%, as is customary in clinical trials of antidepressants, we will enroll a total of 74 subjects, anticipating 60 study completers. Subjects will all be recruited through outpatient psychiatric clinics affiliated with Brigham and Women's Hospital, through physician referral, print advertisements, and flyers.

Inclusion criteria:

- Aged 18-55
- Current diagnosis of major depressive disorder
- Hamilton Depression Rating Scale score of  $\geq 21$

- Stable treatment regimen (no medication changes or changes in psychotherapy treatment in past 8 weeks, and no participation in stepped treatments, such as completion of a course of cognitive behavioral therapy, during the trial)
- Failed to remit with up to 2 sequential antidepressant trials, or combination of 1 antidepressant and 1 augmentation agent
- Women of childbearing age must agree to use an approved method of contraception for the duration of the study

Exclusion criteria:

- Active suicidal ideation
- History of manic episodes or psychosis
- Alcohol or substance use disorder within the past 6 months
- Comorbid neurologic condition affecting the central nervous system
- Comorbid autoimmune condition
- History of thyroid disease or a current abnormal TSH
- Active or recent (within the past month) infection (such as otitis, pneumonia, urinary tract infection); temperature  $> 100.3$  or WBC count  $> 11$  K/microL will be considered evidence of active infection even in the absence of other symptoms
- History of GI bleed
- History of stroke
- History of a bleeding disorder
- Platelet count  $< 150,000/\text{mm}^3$  on initial screening
- On a blood-thinning agent or taking NSAIDs daily
- Current use of oral steroids or other immunomodulating medications
- Salicylate sensitivity
- Pregnancy or breastfeeding
- GFR less than  $60 \text{ mL/min}/1.73\text{m}^2$
- Current use of another nephrotoxic medication

The decision not to restrict participation to subjects utilizing a single medication was made to better reflect clinical practice, in which a variety of SSRI (selective serotonin reuptake inhibitors) and SNRI (serotonin-norepinephrine reuptake inhibitors) are used as first-line agents, and in order to enhance the generalizability of study findings.

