Subjects will be asked to report on their age at first depression diagnosis, and number of depressive episodes, as well as existing treatments for depression, including names and dosages of medications, type(s) of psychotherapy, frequency of meetings with a psychiatrist, psychologist, social worker, or other counselor, and any other treatment modalities they engage in. Female subjects will also be asked to report whether they have regular monthly menstrual cycles, the date of their last menstrual period, and whether they are taking hormonal contraceptives or not. Women of child-bearing age will also receive a qualitative urine HCG pregnancy test. Female subjects will have blood drawn for follicle-stimulating hormone (FSH), estradiol, and progesterone levels. All subjects' temperature will be taken to assess for infection. If their temperature is greater than 100.3F, they will be excluded from the study. Subjects determined to be ineligible based on the results of the screening or screening labs will be thanked for their participation and conclude their participation.

Ten mL of subjects' blood will be separated by centrifuge and the serum analyzed for an array of 60 cytokines and chemokines including C-reactive protein (CRP), interleukin-6 (IL-6), and tumor necrosis factor alpha (TNF-alpha); assays will be performed using a Luminex bead-based immunoassay. Serum will be stored into small aliquots at -80°C to avoid repeated freeze-thaw cycles. 25 µl of serum per subject will be used for Luminex studies as previously reported. Expression data will be analyzed by Luminex software. All samples will be drawn between 8:00 AM and 10:00AM in order to minimize the effect of circadian fluctuations in cytokine levels. Subject's height and weight will be taken to allow for calculation of BMI; prior work has demonstrated a U-shaped relationship between BMI and pro-inflammatory cytokines, with higher values associated with underweight and obesity.

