To evaluate gene profiles of peripheral immune cells, peripheral blood mononuclear cells (PBMCs) will be prepared by Ficoll-Paque PLUS gradient centrifugation from the blood in order to isolate T cells and monocytes. Frequency of CD4+, CD8+, and CD14+ cells will be measured. PBMCs will be stored into aliquots at -80°C. For transcriptomic analysis, Fluidigm Biomark technology will utilize microfluidic technology to perform high throughput gene expression measurements with real time PCR. RNA will be processed from flow cytometry-sorted activated/memory CD4+ (CD3+CD44hi), and CD8+ (CD3+CD44hi) T cells, as well as CD14+ monocytes. A panel of 96 T cell or monocyte-specific genes for pro-inflammatory, anti-inflammatory, chemokine, chemokine receptor, and signaling molecules will be measured.

To allow for the eventual, detailed characterization of the subjects' immunologic profiles, whole blood samples will also be banked for subsequent processing at the [name] Lab at Brigham and Women's Hospital/Harvard Medical School. The samples will be assayed for antigens using the following technique: over 500 individual antigens (proteins, lipids, myelin peptides) are spotted on slides by a robot, after which the slides are incubated with serum from subjects with depression and an immune signature is developed. The samples will also be assayed for microRNAs, non-coding RNAs that modulate immune function.

Subjects who meet inclusion criteria for the study will be given their pill packets for the ensuing 8 weeks, consisting of blister packs for a daily dose of aspirin 325mg in those randomized to the treatment condition and of blister packs of a placebo pill of the same size, shape, and color as the aspirin tablet in those randomized to the control condition. Subjects will be instructed to take

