Of note, and perhaps relevant to all of the above-named antidepressants that are in common use, aspirin is already a commonly given medication for patients with a number of cardiac conditions. Given the prevalence of both cardiovascular disease and depression, it is inevitable that a large number of patients are concurrently being treated with aspirin and a variety of antidepressants. Thus, while the safety of this medication in combination with a range of antidepressants may not have been demonstrated in a clinical trial, there have been ample opportunities for risks associated with these combinations to come to clinical and scientific attention. The lack of publications reporting increased risk is as at least somewhat reassuring as to the relative safety of this combination.

The effect of aspirin on an embryo or fetus can include adverse effects up to and including fetal death. For this reason, women cannot take part in this study if they are pregnant or may become pregnant. While aspirin found in breast milk carries less clear risk, the WHO recommends against long-term therapy; for this reason women cannot take part in this study if they are nursing.

With the blood draws, there are risks of pain and bruising at the phlebotomy site, infection, and lightheadedness.

The assessment of psychiatric history, including depression and substance abuse, can make some people feel uncomfortable as the information is sensitive to some subjects. Some may also be especially concerned about the confidentiality of mental health information. The study staff are trained in mental health assessments, and make every effort to make the subjects comfortable during study visits. All subjects will be assured that their history and responses will be kept confidential within the study, except as required by law, in the case of acute safety concerns, and in any instances as described in the informed consent form.

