## **IX. Monitoring and Quality Assurance:**

The principal investigator, [name], will be responsible for monitoring the safety of all subjects. In the event that [name] is unavailable, physician co-investigators will be available to monitor the safety of all subjects.

All study staff are primarily located at Brigham and Women's Hospital. Study safety meetings, including the principal investigator, study coordinators, and study physicians will occur regularly to review the progress of currently-enrolled subjects and any reported side effects.

The Principal Investigator will assess all patients with regard to stopping criteria. In general terms, a subject will be discontinued from the study for the following reasons:

- 1) The subject has experienced an adverse event that, in the opinion of the principal investigator requires early termination
- 2) The subject's thoughts or behaviors become a safety risk at any time during the trial
- 3) The subject experiences a 20% drop in GFR during the course of the study
- 4) The subject withdraws consent

Specific to this study, subjects will be monitored for suicidal thoughts at both visits and for adverse events as well. Subjects who develop active suicidal ideation, represented by a score of  $>2$  on HDRS item 3, will be referred for urgent or emergent clinical assessment. A patient who develops active suicidal thoughts will be urgently evaluated by a study physician. In any case where there are acute safety concerns arising from suicidality (such as a plan or actual intent), the patient will be sent to the BWH Emergency Department for further evaluation under Section 12a, and in compliance with hospital policies. If there are no acute safety concerns based on the urgent evaluation, the patient will be monitored according to study protocol and instructed to contact study staff immediately with any worsening in their mood or thinking. The study physician will review the urgent or emergent safety assessment and determine if the subject can continue in the study. Any subject who requires a level of care exceeding customary outpatient services (i.e., psychiatric hospitalization or participation in a partial hospital program) will be removed from the study. If a subject must be transferred from the study into clinical care, the study physicians will continue to follow the subjects until they are accepted into appropriate, longer-term care, if clinically indicated.

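### After one pregnancy test at visit 1, where all 8 weeks of pills are dispensed, the protocol relies on agreed contraception and self-report and does not say how an on-study pregnancy is handled

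*Combined protocol and SAP*

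**What the plan says.** All references are to the combined protocol and SAP.

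- **Section VII (Risks and Discomforts)** gives the hazard: "The effect of aspirin on an embryo or fetus can include adverse effects up to and including fetal death". It concludes that "women cannot take part in this study if they are pregnant or may become pregnant".
- **Section III (Subject Selection)** excludes "Pregnancy or breastfeeding" and sets a condition for entry: "Women of childbearing age must agree to use an approved method of contraception for the duration of the study".
- **Section V, Study Visit 1** schedules the one pregnancy test: "Women of child-bearing age will also receive a qualitative urine HCG pregnancy test". The same visit records cycle regularity, date of last menstrual period and use of hormonal contraceptives, and draws FSH, estradiol and progesterone. Eligible subjects "will be given their pill packets for the ensuing 8 weeks".
- **Section V, Study Visits 2 and 3 (weeks 2 and 4)** cover compliance, adverse effects, the SAFTEE, depression scales, cytokines and renal bloods. They may be done remotely without blood draws. No HCG or menstrual-date question is listed.
- **Section V, Study Visit 4 (week 8)** repeats FSH, estradiol and progesterone where appropriate, repeats the SAFTEE, and asks whether the subject's health has changed. No HCG is listed.
- **Section IX (Monitoring and Quality Assurance)** states that "a subject will be discontinued from the study for the following reasons" and lists four: an adverse event that in the principal investigator's opinion requires termination, thoughts or behavior that become a safety risk, a 20% fall in GFR, and withdrawal of consent. Pregnancy is not named.

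**The concern.** The fetal hazard lasts as long as dosing does, but pregnancy status is tested only before dosing starts. A woman who conceives after visit 1, or whose conception was too recent for the visit 1 test to turn positive, meets no later procedure designed to find the pregnancy. If one comes to light, the visible text does not say what follows for study drug, for her participation, or for recording the exposure.

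The protocol treats two other hazards more completely. Renal function and suicidality are each screened at entry, measured again during treatment, and tied to a stated action. Pregnancy, for which the protocol itself names fetal death, is screened at entry only, and no reason is given for the difference. What is at stake is participant and fetal safety, not the efficacy result.

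**Working it through.** The plan gives no figure on this point to reproduce. The check is a comparison of sections, followed by a rough estimate of scale.

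**1. Entry screen, on-treatment check and stated action**

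| Hazard | Entry (Sections III, V) | During dosing (Section V) | Action (Section IX) |
|---|---|---|---|
| Renal | GFR below 60 excluded | BUN and creatinine at weeks 2, 4 and 8 (draws may be omitted at weeks 2 and 4) | 20% fall in GFR is a discontinuation reason |
| Suicidality | Active ideation excluded (HDRS item 3 above 2) | HDRS at weeks 2, 4 and 8 | Urgent evaluation, referral, possible removal |
| Pregnancy | Excluded; one urine HCG; contraception agreed | No scheduled test or menstrual-date question | None named |

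Count: one scheduled pregnancy test at week 0, none at the three later visits, and none of the four listed discontinuation reasons naming pregnancy.

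**2. Expected number of pregnancies on aspirin**

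Inputs from the documents:
- 74 subjects, 37 per group (Section III).
- About 2/3 women (Section IV).
- 8 weeks of dosing (Section V).

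Input assumed: contraceptive failure of 1 to 9% per year. The documents give no rate.

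Formula: expected pregnancies = women × years × yearly rate.

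- Women on aspirin: 37 × 2/3 = 24.7. Both arms: 74 × 2/3 = 49.3.
- Years: 8/52 = 0.154.
- Woman-years on aspirin: 24.7 × 8/52 = 3.79. Both arms: 49.3 × 8/52 = 7.59.
- Expected on aspirin: 3.79 × 0.01 = 0.04, to 3.79 × 0.09 = 0.34.
- Expected in both arms: 7.59 × 0.01 = 0.08, to 7.59 × 0.09 = 0.68.
- Chance of at least one on aspirin (Poisson): 1 − exp(−0.038) = 4%, to 1 − exp(−0.341) = 29%.

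For the assumed rates these are upper-side figures. They treat every woman aged 18 to 55 as able to conceive and every woman as completing 8 weeks, while the plan expects about 20% non-completion.

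**3. Length of exposure**

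A pregnancy beginning at the end of week 1 could be followed by up to 8 − 1 = 7 weeks of dosing, but only if no missed period is noticed and nothing is reported in that time.

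**The case against.** The strongest reply is that the protocol already has a safeguard during treatment. Contraception is required for the whole study, not only at entry, and that can be read as the way Section VII's bar on women who may become pregnant is put into practice. There are also routes to self-report: adverse effects are asked about at weeks 2 and 4, the SAFTEE is completed at each later visit, and week 8 asks about changes in health. The last menstrual period recorded at visit 1 helps to judge whether the urine test was done too early.

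Much of this stands, and it rules out several stronger readings that a reader might infer:

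- *That an on-study pregnancy would certainly be missed.* The documents do not support this, because a woman may notice and report it. They support only that it could go unrecognized.
- *That the bar lapses once dosing begins.* It does not, because the contraception condition continues.
- *That Sections III and VII flatly contradict each other.* The wording is loose rather than clearly contradictory, but it should be aligned.
- *That the stopping list leaves no way to withdraw a pregnant subject.* Section IX presents the list as general and itself adds a removal reason outside the four (need for care above outpatient level). The first reason gives the principal investigator discretion over adverse events. However, nothing visible classes pregnancy as an adverse event.
- *That the cytokine and hormone results would be distorted.* The documents do not quantify this, and with fewer than one pregnancy expected among 74 subjects it is negligible.

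The consent pages are not available for review, so any instruction there to report a pregnancy cannot be seen.

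What the reply leaves open is detection. Contraception lowers the chance of pregnancy but does not reveal one, no later visit lists a check that it continues, and a woman cannot report a pregnancy she has not recognized.

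**Conclusion.** The point holds as a safety gap of low probability and serious consequence. After visit 1 the visible protocol depends on agreed contraception and self-report, schedules no recheck of pregnancy status while subjects are dosing, and does not state how a pregnancy found on study is handled. On the assumed failure rates the expected number on aspirin is at most about 0.04 to 0.34, so the most likely outcome is none. The case for a change rests on the severity of the harm that the protocol itself names and on the low cost of a recheck, not on frequency. The sample size and the primary HDRS analysis are unaffected.

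**What to change.** - Reconcile Section III (exclusion and contraception), Section V (visit 1 and the later visits), Section VII (the bar) and Section IX (discontinuation). In particular, state what Section VII's wording on women who may become pregnant means for women using contraception.
- Add a recheck of pregnancy status during dosing for women of childbearing age, at contacts already planned. Two options are to ask the date of the last menstrual period, which also works at remote visits, or to run HCG on blood already drawn, which does not work where the draw is omitted. The sponsor should set the timing, bearing in mind that a check at week 8 comes when dosing ends.
- Have the sponsor state in Section IX how the Section VII restriction applies to a pregnancy found on study. The content of that rule is the sponsor's decision.

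The cost is protocol wording, one added question and, if HCG is chosen, a small assay charge. Even at all three later visits the number of assays would be at most about 49 × 3 = 147. No visit is added.

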### **VIII. Potential Benefits:**

No benefits can be guaranteed from participation in the study. However, half of all enrolled participants will be receiving an adjunctive agent that is hypothesized to help treat their

depression, and it is possible that at least some subjects will experience a decrease in the severity of their self-reported depression symptoms. In addition, even those receiving placebo may benefit from the placebo effect and from the attention of the study staff. In addition, all subjects will be permitted to continue their existing psychiatric treatments. The results of this study also have potential to benefit larger clinical populations if it is identified that aspirin is an effective adjunctive treatment for depression. Further, the data collected during the study will expand our knowledge of the role of immune biomarkers in depression and treatment response.

## **IX. Monitoring and Quality Assurance:**

The principal investigator, [name], will be responsible for monitoring the safety of all subjects. In the event that [name] is unavailable, physician co-investigators will be available to monitor the safety of all subjects.

All study staff are primarily located at Brigham and Women's Hospital. Study safety meetings, including the principal investigator, study coordinators, and study physicians will occur regularly to review the progress of currently-enrolled subjects and any reported side effects.

The Principal Investigator will assess all patients with regard to stopping criteria. In general terms, a subject will be discontinued from the study for the following reasons:

- 1) The subject has experienced an adverse event that, in the opinion of the principal investigator requires early termination
- 2) The subject's thoughts or behaviors become a safety risk at any time during the trial
- 3) The subject experiences a 20% drop in GFR during the course of the study
- 4) The subject withdraws consent

Specific to this study, subjects will be monitored for suicidal thoughts at both visits and for adverse events as well. Subjects who develop active suicidal ideation, represented by a score of  $>2$  on HDRS item 3, will be referred for urgent or emergent clinical assessment. A patient who develops active suicidal thoughts will be urgently evaluated by a study physician. In any case where there are acute safety concerns arising from suicidality (such as a plan or actual intent), the patient will be sent to the BWH Emergency Department for further evaluation under Section 12a, and in compliance with hospital policies. If there are no acute safety concerns based on the urgent evaluation, the patient will be monitored according to study protocol and instructed to contact study staff immediately with any worsening in their mood or thinking. The study physician will review the urgent or emergent safety assessment and determine if the subject can continue in the study. Any subject who requires a level of care exceeding customary outpatient services (i.e., psychiatric hospitalization or participation in a partial hospital program) will be removed from the study. If a subject must be transferred from the study into clinical care, the study physicians will continue to follow the subjects until they are accepted into appropriate, longer-term care, if clinically indicated.

Any subject who discontinues the study due to adverse effects arising during the study will be advised to follow up with their primary care physician. If an adverse event occurs, or there is an

abnormal finding during laboratory testing, that information will be released to the subject's primary physician with the subject's permission and written release.

At the end of the study, study staff will arrange for any additional (or new) psychiatric follow up, as clinically indicated.

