their pills in the evening before bed; in cardiovascular studies aspirin has had greater efficacy and better tolerability when taken at this time of day. Subjects will be instructed not to take aspirin over the counter during the study, and to inform study staff of their use of other over-the-counter anti-inflammatory medications. All subjects will be instructed to also continue their existing antidepressant treatment regimen but not to engage in new treatments or therapies during the course of the study. If new treatments are deemed clinically necessary during the course of the study subjects are instructed to contact study staff immediately to inform them of the change.

Study Visit 2 and 3 (weeks 2 and 4):

At study visits 2 and 3, subjects will be asked about their compliance with the study drug and about any adverse effects; they also will again complete the SAFTEE. They will be asked about any changes to their medications or psychiatric treatment. Study staff will re-administer the Hamilton Depression Rating Scale (HDRS) and subjects will again complete the QIDS-SR. Blood will be drawn for repeat cytokine/chemokine immunoassay, BUN, creatinine, and electrolytes measurements. If preferred, the subject can complete the psychometric measures by telephone and online portal and omit the blood draws at these visits.

Study Visit 4 (week 8):

At study visit 4, study staff will re-administer the Hamilton Depression Rating Scale (HDRS) and blood will again be drawn for repeat cytokine/chemokine immunoassay, including measures of CRP, IL-6, BUN, creatinine, electrolytes and TNF-alpha. Subjects will again complete the QIDS-SR and the SAFTEE, and will be asked about any changes to their medications or psychiatric treatment and any changes in their health status. Platelet count and FSH, estradiol, and progesterone levels as appropriate, will also be repeated. Follow up samples for the detailed immunologic profiling will also be drawn. Serum salicylate concentrations will be drawn (to confirm compliance with study medication in those subjects assigned to the aspirin condition, and to confirm subjects not assigned to the aspirin condition were not using it).

Subjects will be advised to follow up with their current outpatient psychiatric providers within two weeks of ending participation in the study.

Remuneration:

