## **VI. Biostatistical Analyses:**

The baseline data to be collected and analyzed include: subject age at enrollment, gender, age of depression onset, number of previous depressive episodes, HDRS. HDRS will be repeated at the subsequent study visits for analysis. Cytokine levels will also be analyzed at the initial and final visits. The planned study end-point is at eight weeks after initiation, and is not based on any pre-determined treatment response. Exploratory analysis of the immunologic profiling data will be performed as well, with a goal to detect within-subject changes over the course of the study and to discern any differences between non-responders and responders.

Baseline measurements for continuous variables (e.g., age of onset, current age) will be assessed by t-test. Categorical measurements, such as gender, will be compared with Fisher's exact test or chi-square as appropriate. For the primary study outcome, the change in HDRS in the treatment versus control groups will be evaluated with analysis of covariance (ANCOVA), with initial HDRS score as a covariate.

Power calculations were based on a prior open-label trial of salicylic acid as an augmentation agent to fluoxetine, which found an average 15-point drop in HDRS score over a 4-week trial. To be conservative, we are assuming a much smaller effect size, and so this study is powered to detect a 3-point difference in HDRS score, a difference which is deemed to be clinically significant. 29 participants per group are required to detect this clinically significant difference assuming .80 power and a two-sided alpha of 0.05. Assuming a non-completion rate of approximately 20%, customary in clinical trials of antidepressants, we will enroll 74 subjects, anticipating 60 completers.

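### Section IX takes subjects who stop for harm or worsening out of the study, not just off study drug, and provides for no outcome collection afterwards

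*Combined protocol and SAP*

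**What the plan says.** Section IX introduces its list of stopping criteria with "In general terms, a subject will be discontinued from the study for the following reasons". Three of the four criteria concern harm or worsening: "The subject has experienced an adverse event that, in the opinion of the principal investigator requires early termination"; "The subject's thoughts or behaviors become a safety risk at any time during the trial"; and "The subject experiences a 20% drop in GFR during the course of the study". The fourth is withdrawal of consent. A later sentence covers subjects who need more than outpatient care; it reads in part "i.e., psychiatric hospitalization or participation in a partial hospital program) will be removed from the study".

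The follow-up described after these exits is clinical. "Any subject who discontinues the study due to adverse effects arising during the study will be advised to follow up with their primary care physician". For subjects transferred into clinical care, the study physicians keep contact until another service takes over, where clinically needed. No rating is named in either case.

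Section V schedules HDRS, QIDS-SR and SAFTEE at weeks 2, 4 and 8, the last at Study Visit 4. For Study Visits 2 and 3 only, it adds: "If preferred, the subject can complete the psychometric measures by telephone and online portal and omit the blood draws at these visits". Section VI fixes the time point: "The planned study end-point is at eight weeks after initiation, and is not based on any pre-determined treatment response". The primary analysis is an ANCOVA of HDRS change with baseline HDRS as covariate, and the main biomarker models use HDRS change from V1 to V4.

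**The concern.** The plan has no status for a subject who has stopped the tablets but is still being assessed. Read as written, a subject taken off aspirin at week 3 for bleeding, or admitted at week 5, leaves the trial with no further HDRS, QIDS-SR or SAFTEE.

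These subjects are not a random subset. Safety-risk and higher-care exits take out poor depression outcomes. Adverse-event exits may fall more on aspirin, since section VII treats bleeding as its main hazard and describes added upper GI bleeding risk with SSRIs. The week-8 contrast could then compare two groups of remaining subjects selected in different ways. The baseline-cytokine-by-treatment models share the problem, because they need the same week-8 HDRS. For events between visits, the tolerability comparison also lacks a SAFTEE at and after the event.

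**Working it through.** **1. Routes out of the study, side by side**

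| Route (section IX) | Stated consequence | Ratings provided for afterwards |
|---|---|---|
| Adverse event | Leaves the study | None; primary-care advice |
| Safety-risk thoughts or behaviours | Leaves the study | None; clinical hand-over if transferred |
| 20% GFR drop | Leaves the study | None, but see below |
| Hospital or partial-hospital care | Leaves the study | None; clinical hand-over |
| Withdrawal of consent | Leaves the study | None, properly |
| HDRS item 3 above 2, alone | Urgent assessment; study physician decides | Continues if allowed to stay |

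The scheduled creatinine draws are at Visits 2, 3 and 4, where the ratings are also due. A GFR drop found at one of these visits therefore comes with ratings from that visit, and a drop found at Visit 4 costs no week-8 score. The defect lies in the first four rows.

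**2. The plan's own figures (sections III and VI)**

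- Inputs: 29 per group, about 20% non-completion.
- 29 / 0.8 = 36.25, rounded up to 37 per group, so 74 in total. This reproduces the plan.
- 74 × 0.8 = 59.2, in line with the stated 60 completers.
- 74 − 60 = 14 expected non-completers. The plan does not divide these by reason or by arm.

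**3. Illustrative bias in a comparison of those still observed at week 8**

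Let m be the share of an arm that leaves, and D the number of HDRS points by which leavers would have scored worse than completers. Completers in an arm then look better than the whole arm by m × D. For aspirin minus placebo, where lower is better:

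bias = m(placebo) × D(placebo) − m(aspirin) × D(aspirin)

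The documents give neither m by arm nor D. All values below are assumptions.

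| Assumed loss, aspirin / placebo | Assumed gap D | Bias | Favours |
|---|---|---|---|
| 20% / 20% | same in both arms | 0 | neither |
| 25% / 15% | 3, 5, 8 in both arms | −0.3, −0.5, −0.8 | aspirin |
| 30% / 10% | 3, 5, 8 in both arms | −0.6, −1.0, −1.6 | aspirin |
| 20% / 20% | 3 to 8 in placebo, 0 in aspirin | 0.2 × 3 = +0.6 to 0.2 × 8 = +1.6 | placebo |

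The bias is proportional to the share leaving for these reasons. In the last row, if only 10% of the placebo arm left through worsening, it would be 0.1 × 3 = 0.3 to 0.1 × 8 = 0.8 points.

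**4. Power if those who stop drug are still rated**

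The plan states no SD. Solving back from 3 points, 29 per group, 80% power and two-sided 0.05 gives about 4.0 by the t-test (4.1 by the normal approximation). Assume SD 4.0, all 37 per arm observed, and 20% off drug retaining a share s of the effect. The mean effect is 3 × (0.8 + 0.2s).

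- s = 0: 2.4 points, power 0.72
- s = 0.5: 2.7 points, power 0.82
- s = 1: 3.0 points, power 0.89

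For comparison, 30 completers per arm with the full 3 points give 0.815. Power may therefore fall or rise.

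**The case against.** The strongest reply is that the protocol nowhere says the later scores are withheld. The section IX list is framed as general, section V relies on a safety plan not reproduced in the protocol, and the consent form may say more. That stands as a limit: the data loss is inferred. But section IX is not merely silent. It states that these subjects leave the study, and no section provides for outcome data from someone who has left.

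Several stronger readings are tempting and are not supported:

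- **That every criterion is at fault.** Withdrawn consent properly ends collection. Item 3 above 2 does not by itself remove anyone. Section V asks subjects who need new treatment to tell staff, and this is not listed as a ground for removal, so worsening managed as an outpatient can stay in the data.
- **That SAFTEE is missing at every stopping event.** Not for a GFR drop found at a scheduled visit.
- **That remote rating already covers week 8.** It is offered at Visits 2 and 3 only. It suggests feasibility but would have to be extended.
- **That the bias runs against aspirin, or for it.** Equal loss with equal gaps gives none, and other plausible patterns give either sign. The 20% is also general non-completion, part of which may be withdrawal or loss to follow-up that this change cannot recover. Section VI names no completer analysis set, and week 2 and 4 scores will exist for many leavers. An analysis using them could reduce the bias, but could not supply the week-8 scores.
- **That retrieval brings a clear gain in precision.** If 7 of the 14 were rated, the standard error would fall by about 5% (√(60/67) = 0.946). If those 7 split evenly between arms and carried no drug effect, the contrast would shrink to 30/33.5 = 0.896 of its size. Signal to noise would be 0.896/0.946 = 0.947, a loss of about 5%.

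**Conclusion.** The concern holds for four routes: adverse event, safety risk, 20% GFR drop and higher level of care. Followed as written, section IX ends study participation for these subjects, and the protocol provides no outcome assessment at stopping or afterwards. That the remaining ratings, including week 8, are not obtained is an inference from those two facts.

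The consequence is possible selection bias of unknown direction in the week-8 HDRS ANCOVA and the V1-to-V4 biomarker models. Under the assumed gaps and losses it runs from 0 to about 1.6 points either way, up to about half of the 3-point target (1.6/3 = 0.53). This is an illustration of scale, not an estimate, because the number leaving by these routes is not stated. The change is worth making because it is cheap and because scores never taken cannot be recovered by analysis.

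**What to change.** Leave the clinical stopping criteria and care decisions unchanged. In section IX:

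1. Define two separate states, *study drug stopped* and *withdrawn from the study*, and reserve the second for subjects who withdraw consent to follow-up.
2. Reword the sentence introducing the criteria and the higher-care sentence so that they end study treatment, not outcome collection. Without this, the present wording would contradict continued follow-up.
3. Seek HDRS and SAFTEE at the time of stopping when this falls between visits.
4. Seek HDRS, QIDS-SR and SAFTEE at the remaining scheduled weeks, including week 8, from all who still consent.

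In section V, extend the telephone and portal option to week 8 for these subjects. A remote week-8 HDRS is enough for the primary ANCOVA and for the models using baseline cytokines. Week-8 cytokine comparisons would still need a blood draw.

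The cost is protocol and consent wording and a few extra ratings by existing staff. Uptake will be incomplete, particularly among hospitalised subjects. Some retained scores will reflect time off drug or other care and may dilute the contrast, which is why power could lie anywhere from about 0.72 to 0.89 under the assumptions above.
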